12.2 Sample Size/Accrual Rate

The sample size for this trial will be based on statistical selection theory criterion as described by Simon et al.⁷⁷ For a selection trial, one simply chooses the regimen that results in the "best" response. While Simon used this idea in the context of choosing the regimen with the best tumor response, the idea is applicable to outcomes with other distributions (in addition to the binomial). In our trial, the response is self-reported anxiety, which we will assume is normally distributed, so the best regimen will be the one with the lowest mean anxiety score. We will proceed to a phase III trial if one of the RESPeRATE intervention arms results in the least anxiety, and the mean anxiety score in that group is at least 0.5 standard deviations (SD) less than mean anxiety score in the control group. The sample size is chosen to ensure a high probability of selecting the best arm, assuming that the mean anxiety score in the low dose arm is 0.5 SD less than the mean in the control group and the mean anxiety score in the high dose arm is 1.0 SD less than the mean in the control arm. Under these assumptions, we used

simulations to determine the sample size needed in each group to ensure that the probability of selecting the best regimen was 90%. We randomly selected n independent observations from the normal distribution with an SD = 1, calculated the mean anxiety scores for each group, and selected the group with the least observed mean. This was repeated 200,000 times. The probability that the best regimen was chosen is calculated as the proportion of times (of the 200,000 repetitions) that the group with the true lowest mean was selected. In addition to selecting the best regimen, we will only pursue a subsequent phase III trial if there is some evidence of effect. Thus, we will require that the mean in the best regimen is at least 0.5 SD lower than the mean for the control group. Using simulations, we find that 20 patients per group provides 90% probability that the best regimen will be chosen and the mean in that group be at least 0.5 SD lower than the mean in the control arm. Assuming a 20% dropout, we will accrue a total of 75 participants to this study (20x3/.8). Assuming no effect of the RESPeRATE device, we have 90% probability of stopping with the phase II trial.

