12.4 Primary Endpoint(s)

The primary objective of this study is to collect data that will allow us to assess the feasibility of conducting a phase III randomized study of device-guided breathing in lung cancer survivors with significant anxiety. These endpoints include: participation, accrual, adherence, and retention.

The participation rate will be calculated as the proportion of eligible patients who agree to participate.

The accrual rate will be calculated as the number of patients accrued to the study divided by the number of months of accrual.

The actual amount of time the participant used the device will be retrieved from each device. Adherence will be calculated as the actual amount of time the device is used divided by the prescribed time. Successful adherence will be defined as use of the device $\geq 75\%$ of the time assigned. We will also estimate the proportion of patients who use the device more than prescribed. (If “low-dose” participants use the device more than prescribed, this may limit our ability to detect a dose effect.)

Retention will be calculated as the number of participants who complete the final assessment divided by number randomized.

Confidence intervals for the binomial proportions will be calculated using methods described by Wilson.⁷⁸ Approximate 95% confidence intervals based on the normal distribution will be calculated for the continuous measures.

The clinical endpoints are anxiety (primary outcome: anxiety subscale of the HADS-Anxiety/Depression Scale), cancer-related worry, dyspnea, and pulmonary function at baseline and 6 and 12 weeks post-randomization. Estimates of treatment efficacy will be obtained using the “intent to treat” approach. Descriptive statistics (means, standard deviations, frequencies,

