etc.) will be presented for each outcome measure at baseline and follow-up points stratified by treatment arm. Repeated measures (RM) ANCOVA models (fitted using PROC MIXED in SAS) will estimate the treatment effect for each outcome, test for treatment differences, and obtain adjusted post-treatment estimates of the variability of these outcomes. Estimates of outcome measure variability will be used to determine sample size for the subsequent trial. The primary RM ANCOVA model will include time, treatment arm, and the stratification factors. An unstructured covariance matrix will be used to account for the within-patient correlation over time. In secondary models, additional covariance structures (Toeplitz, Autoregressive, Compound Symmetry) will be assessed and the optimal structure will be chosen based on likelihood ratio tests for nested structures and the BIC statistic for non-nested structures. Least squares means and 95% confidence intervals will be provided for each outcome, stratified by treatment arm, and for the difference between treatment arms. Regression diagnostics and residual plots will be used to find appropriate transformations for variables in the model.

Subsequent RM ANCOVA models will include additional covariates (e.g., age, sex, stage) to correct for chance imbalances in important prognostic variables and account for variability in outcome measures due to covariates. These latter models will inform us of possible stratification factors for the subsequent trial. Limited exploratory analyses will be done to determine if the treatment effect differs for different levels of covariates (e.g., by including treatment by covariate interactions in the model) to see if the subsequent trial should be done in particular subsets of lung cancer survivors. It is likely that some data will be missing. In addition to the mixed models above, we will use multiple imputation pattern-mixture models under various assumptions (e.g., participants in the active arms who drop out would have subsequent patterns similar to participants in the control arm) to assess the sensitivity of our modeling assumptions.

The optimal dose will be defined as the one that results in the greatest improvement in anxiety scores at 12 weeks (based on estimates from the RM ANCOVA model). This dose will be used in the subsequent trial, assuming that it is one of the RESPeRATE intervention groups.

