Assuming the 95% confidence interval for the treatment effect includes a clinically meaningful difference, the sample size for the subsequent phase III trial will be determined based on detecting a clinically meaningful difference with a high power using estimates of variability obtained in this study. The estimates of retention and adherence observed in this study will be used to refine that sample size estimate. Subsequent trial feasibility will be assessed based on our ability to recruit the required number of participants. For that, we will use the accrual and participation rates observed in the participating sites. For sites that did not participate in this pilot study, accrual will be estimated by multiplying the estimated number of eligible patients times the participation rate across the participating sites.

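### Does Section 12.4 replace the 0.5 SD go rule of Section 12.2 with a looser or conflicting confidence-interval condition?

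*Combined protocol and SAP*

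**What the plan says.** Section 12.2 (Sample Size/Accrual Rate) states the go decision. A RESPeRATE arm must come out best on anxiety, and a margin over control is set as well: "the mean anxiety score in that group is at least 0.5 standard deviations (SD) less than mean anxiety score in the control group". It adds that "we will only pursue a subsequent phase III trial if there is some evidence of effect" and then that "we will require that the mean in the best regimen is at least 0.5 SD lower than the mean for the control group". The 20 evaluable patients per arm, the total of 75 after 20% dropout and two operating characteristics go with that rule. The first is a 90% chance of choosing the best arm with the margin met, if the true effects are 0.5 SD (low dose) and 1.0 SD (high dose). The second is "Assuming no effect of the RESPeRATE device, we have 90% probability of stopping with the phase II trial".

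Section 12.4 (Primary Endpoint(s)) returns to the next trial after describing the repeated-measures model. The dose with the greatest 12-week improvement in anxiety is taken as optimal, and "This dose will be used in the subsequent trial, assuming that it is one of the RESPeRATE intervention groups". The following paragraph opens with "Assuming the 95% confidence interval for the treatment effect includes a clinically meaningful difference, the sample size for the subsequent phase III trial" and goes on to the variability, retention, adherence, participation and accrual estimates that will feed the sizing and feasibility assessment. The section neither restates nor revokes the 0.5 SD margin, gives no value for the meaningful difference, and does not name the arms that the interval compares.

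**The concern.** An analyst who opens 12.4 to learn how the dose decision is made finds the best-arm test without the margin, plus an interval condition that 12.2 never mentions. Three worries follow.

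- The 90% stopping figure depends on the margin. If 12.4 were the operative rule, that figure would not describe it.
- Taken word for word, an interval *includes* a threshold only if the threshold lies between its limits. A very strong result, with the whole interval above the threshold, would then fail.
- The threshold has no value, and 12.2 does not say which SD defines 0.5 SD, although 12.4 will also "obtain adjusted post-treatment estimates of the variability of these outcomes". That could leave room to settle the go decision after the results are known.

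Feasibility is the primary aim, but dose selection is Objective 3 and the sample size was derived from the selection rule. A real conflict would undermine the stated justification for 75 patients.

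**Working it through.** **Inputs.** From 12.2: n = 20 evaluable per arm, SD = 1, margin 0.5 SD, true effects 0.5 and 1.0 SD under the planned alternative, and zero in both arms under no effect. From 12.4: a 95% interval, for which normal-theory limits are used here. The meaningful difference M is not in the documents, so it is an assumption and is varied from 0.3 to 1.2 SD.

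**Step 1: reproduce 12.2.** The standard error of a difference between two arms is √(2/20) = 0.316 SD. The two differences that matter, control minus high dose and low dose minus high dose, share the high-dose mean and so have correlation 0.5.

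- Planned alternative: P(high dose lowest and at least 0.5 SD below control) = 0.901 from the exact bivariate normal.
- No effect: P(stop) = 1 − 2 × P(a given active arm is lowest and at least 0.5 SD below control) = 0.901.
- Total: 20 × 3 / 0.8 = 75.

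All three match the plan.

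**Step 2: width of the interval.** 1.96 × 0.316 = 0.62 SD (0.63 with a t quantile on 57 degrees of freedom).

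**Step 3: both sections applied, interval read as not ruling out M.** The condition is that the observed difference d satisfies d + 0.62 ≥ M. Section 12.2 already requires d ≥ 0.5, so d + 0.62 ≥ 1.12. The interval condition therefore holds automatically for every M up to 1.12 SD. Simulation with 2,000,000 trials agrees: selecting the high dose and proceeding stays at 0.901 for M up to 1.1 SD and is 0.871 at 1.2 SD. Stopping under no effect stays at 0.901 over the same range and rises beyond it.

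**Step 4: both sections applied, interval required to straddle M.**

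| M (SD, assumed) | P(high dose and go), planned alternative |
|---|---|
| 0.3 | 0.31 |
| 0.5 | 0.55 |
| 0.8 | 0.81 |
| 1.0 | 0.88 |
| 1.2 | 0.87 |

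Stopping under no effect remains at about 0.90 or higher. The loss at M = 0.5 comes from trials whose selected-arm interval lies entirely above 0.5 SD: 36% of all trials under the planned alternative, counting either active arm.

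**Step 5: 12.4 applied alone, 12.2 ignored.** With only the best-arm test, an active arm is lowest two times in three under no effect, so P(stop) = 0.33. Adding the interval condition gives about 0.33 to 0.34 at M = 0.3 to 0.5, 0.58 at 0.8, 0.81 at 1.0 and 0.94 at 1.2 SD.

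**Step 6: which SD.** With an estimated SD, and baseline correlations of 0, 0.5 and 0.7 assumed for a baseline-adjusted analysis:

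| SD used for the margin | Stop under no effect | High dose and go |
|---|---|---|
| Raw | 0.897 / 0.935 / 0.972 | 0.900 / 0.938 / 0.974 |
| Model-adjusted | 0.896 / 0.897 / 0.896 | 0.900 / 0.951 / 0.985 |

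Either choice keeps both probabilities at about 90% or higher.

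**Step 7: which reading fits the text.** Section 12.2 uses *only* and *require* about going to phase III. The sentences in 12.4 have different subjects: the dose to be carried forward, and how the next sample size will be determined. They can be followed after the 12.2 decision without contradicting it. The condition also refers to *a* clinically meaningful difference. Every value in an interval lying wholly above the threshold is clinically meaningful, so such an interval does include one. Step 3 is therefore the natural reading; Step 4 would make the strongest results fail, and Step 5 sets aside an explicit requirement.

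**The case for a change.** The best case for a change is that the plan states a numerical rule with operating characteristics and builds its sample size on it, while the section an analyst will actually work from omits that rule. Section 12.4 never says that 12.2 comes first, and an undefined threshold leaves discretion once results are known. Taken strictly, a trial that passes 12.2 with its interval wholly above the threshold has no stated route to a phase III sample size.

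The textual observations stand: the margin is not repeated, there is no cross-reference, the threshold has no value, and the wording of the interval condition is loose. The consequence does not follow. Both passages belong to Section 12, and the go rule is stated there as a requirement. The discretion over the threshold cannot loosen the decision, because the interval condition is an extra requirement on top of the margin; for any threshold up to about 1.12 SD it does not bind at all. The contrast is also easy to infer: the condition follows directly on selection of the dose, and 12.4 already provides intervals for differences between arms, so selected dose against control is the obvious comparison. The meaningful difference is needed when the next trial is sized, and it can be justified in that trial's own protocol.

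**Conclusion.** This is a gap that analysts fill sensibly, with some loose wording. Read as a whole, Section 12 gives one sound decision rule: proceed only if a RESPeRATE arm is best and at least 0.5 SD below control, then carry that dose forward and size the next trial, provided that a meaningful difference has not been ruled out. Under that reading the stated 90% selection and 90% stopping both hold (0.901 each), unchanged for any meaningful difference up to about 1.12 SD. The figures of 55% selection and 33% stopping are arithmetically correct, but the first needs a strained reading plus an assumed threshold of 0.5 SD, and the second needs 12.2 to be disregarded.

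A cross-reference, a named SD or a stated threshold would be tidier, but would only write down what a reader of both sections would already do. Deleting the interval condition would remove something redundant. None of these alters an estimate, a test, the sample size or the go decision. The conclusion rests on 20 evaluable patients per arm, normally distributed scores as assumed in 12.2, and a meaningful difference no larger than about 1.12 SD.

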12.5 Secondary Endpoint(s)

Epigenetic and Gene Expression Analyses.

To characterize the DNA methylation and gene expression patterns between the different groups, mixed effects models will be used. Changes of methylation or expression levels will be treated as the dependent variables and the intervention groups will be the independent variable of interest. Baseline methylation or expression levels, age, chip, chip position, and other covariates will be adjusted in the model. After comparing the fit of these data at a set of 20 random CpG markers (for the methylation analysis only), the alternative paired difference between baseline and twelve weeks (percent change dividing the difference by baseline value) will be examined to see if it provides a better fit to these data.

To determine if changes in anxiety are associated with methylation or gene expression patterns, mixed effects models will be used, and changes in anxiety variables will be treated as the dependent variables. Baseline methylation or expression, change of methylation or expression,

intervention group, and interaction between intervention group and change of methylation or expression will be included in the model, along with the appropriate covariates. If the interaction effect is significant, it means that the association between the change in anxiety and change in methylation or expression proportion is not the same between the two exposure groups. Multiple comparisons will be adjusted using Bonferroni correction as before.

Salivary Cortisol Analyses. Participants with endocrine disorders (e.g., diabetes and thyroid disorders) or on steroid-based medications are excluded from the cortisol portion of the study (topical hydrocortisone cream permitted). Cortisol levels will be assessed upon awakening, 30 minutes post-awakening, and at bedtime for three consecutive days at baseline and three consecutive days at 12 weeks. Several measures will be derived from the three daily cortisol values, including the mean levels at each time, the mean cortisol awakening response (CAR – change in cortisol from awakening to 30 minutes), the area under the curve (AUC), and the diurnal slope (change in cortisol between awakening and bedtime). Scatterplots and correlations will be used to quantitate the associations between these measures, and anxiety at each time (baseline and 12 weeks) as well as association between the change in cortisol measures and the change in anxiety. Additionally, mixed effects models, as described above, will be used to assess the association between baseline cortisol and changes in anxiety over time. To assess group differences in cortisol parameters, each of these measures at 12 weeks will be used as dependent variables in analysis of covariance models, using appropriate transformations as needed. Baseline levels of the measures will be used as covariates along with treatment group.

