1. OBJECTIVES

1.1. To assess feasibility (accrual, participation, adherence, retention) of a randomized study of device-guided breathing in 75 post-treatment lung cancer survivors with significant anxiety.

1.2. To obtain preliminary data on the variability and efficacy of two doses of a device-guided breathing intervention versus a usual breathing control group for reducing anxiety (primary outcome) and for improving self-reported cancer-related worry, dyspnea and respiratory functioning (secondary outcomes) in post-treatment lung cancer survivors.

1.3. To select the optimal dose of the device-guided breathing intervention (15 minutes once/day or twice/day) for subsequent randomized study.

1.4. Supplemental Objective: To determine if changes in anxiety attributed to device-guided breathing are correlated with epigenetic (DNA methylation) and/or gene expression changes.

1.5. Supplemental Objective: To obtain preliminary data on changes in salivary cortisol (diurnal slope, cortisol awakening response, area under the curve) in each intervention group and associations between salivary cortisol and anxiety.

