Materials for saliva collection will be distributed to participants at baseline. Materials can be provided in-person at the clinic visit or the materials can be shipped to the participant's home. Participants will collect saliva samples three times a day (at awakening, 30 minutes post-awakening, and bedtime) for three consecutive days following baseline and three consecutive days following the Week 12 follow-up visit. Saliva samples are collected by placing a cotton roll under the tongue for approximately 1-2 minutes which is subsequently stored in a plastic tube and refrigerated. Participants will be instructed to refrain from eating, drinking, smoking, brushing their teeth, using mouthwash, or engaging in exercise or similar physical activity for 30 minutes prior to saliva collection. Participants will be provided with saliva collection diaries to record compliance to these behaviors as well as the time in which their saliva samples were collected. After all nine samples have been collected at each time point (baseline, Week 12 follow-up), participants may return their samples and saliva collection diaries by: 1) returning them to the local clinic within 2 weeks of collection and the local clinic will take responsibility for sending them to Wake Forest NCORP Research Base, or 2) using pre-paid postage to return their samples and saliva collection diaries directly to the Wake Forest NCORP Research Base. Once received at the Wake Forest NCORP Research Base, all samples will be refrigerated (-80° C) until assayed.

Samples will be assayed in duplicate at Wake Forest NCORP Research Base using The Salimetrics® Cortisol Enzyme Immunoassay Kit (State College, PA). At no time in the testing process are samples identified by name of subject or any information that would link the sample directly to an individual. On the day of analysis, samples are thawed at room temperature (20 to 22°C), centrifuged (1500 x g) for 15 minutes and assayed. The test used 25 µL of saliva per determination, has a lower limit of sensitivity of 0.003 µg/dL, standard curve range from 0.012 µg/dL to 3.0 µg/dL, an average intra-assay coefficient of variation of 3.5% and an average inter-assay coefficient of variation of 5.1%. Method accuracy determined by spike and recovery averaged 100.8% and linearity determined by serial dilution averaged 91.7%. Values from matched serum and saliva samples show the expected strong linear relationship, $r (47) = 0.91$, $p < 0.0001$.

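### The cortisol diurnal slope is written as a plain awakening-to-bedtime difference, so the length of the waking day is mixed into the measure

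*Combined protocol and SAP*

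**What the plan says.** Objective 1.5 is supplemental: "To obtain preliminary data on changes in salivary cortisol (diurnal slope, cortisol awakening response, area under the curve) in each intervention group", together with associations between cortisol and anxiety. Section 12.1 repeats the objective. Neither place defines the slope.

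The only definition is in the salivary cortisol paragraph of Section 12.5. The sampling scheme is "Cortisol levels will be assessed upon awakening, 30 minutes post-awakening, and at bedtime for three consecutive days at baseline", and the same again at 12 weeks. Then "Several measures will be derived from the three daily cortisol values", among them "the diurnal slope (change in cortisol between awakening and bedtime". The awakening response is also a raw change, "change in cortisol from awakening to 30 minutes", but over a nominally fixed interval. The area under the curve has no formula.

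Each measure is to be correlated with anxiety at baseline and at 12 weeks, and change with change. The arms are compared by analysis of covariance on the 12-week values: "Baseline levels of the measures will be used as covariates along with treatment group". Waking span, wake time and bedtime do not appear in that model.

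Section 7.5.3 gives participants a diary in which to "record compliance to these behaviors as well as the time in which their saliva samples were collected". No section says that these times enter the slope.

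**The concern.** A slope is a change per unit of time. What Section 12.5 describes is a change in µg/dL between two events, waking and going to bed, whose separation differs between people, between days and between visits. The quantity therefore combines how fast cortisol falls with how long the person was awake. Only the first is the rhythm the objective is about.

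Two uses are at stake. In the arm comparison at 12 weeks, variation in waking span inflates the residual variance in a small sample: 75 × 0.8 = 60 participants after the planned 20% attrition, before the endocrine and steroid exclusions, whose number is not given. In the correlations with anxiety, randomisation offers no protection. If more anxious participants keep shorter or longer days, a correlation can arise from sleep timing alone.

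**Working it through.** The documents state no figure for the slope, so there is nothing to reproduce. The check is a reading of the text followed by an illustration on assumed inputs.

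**Text.** The definition in Section 12.5 is a difference. Sections 1, 7.2, 7.4, 7.5.3, 12.1 and 12.5 contain no division by elapsed hours, no regression on clock time and no adjustment for waking span. The collection times are available from the diary in Section 7.5.3.

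**Assumed inputs (not in the documents).** Waking spans of 13 to 18 hours. Either a linear decline at hourly rate b, or an exponential decline C(t) = C0·exp(−kt) with k = 0.05 to 0.15 per hour.

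**Formulas, for two people with the same rhythm and spans T1 < T2.**
- Linear, raw change: b·T, so the spurious relative difference is T2/T1 − 1.
- Exponential, raw change: C0·(1 − exp(−kT)), so it is (1 − exp(−k·T2))/(1 − exp(−k·T1)) − 1.
- Exponential, raw change per hour: the exponential ratio multiplied by T1/T2, minus 1.
- Exponential, log slope: [ln C(T) − ln C(0)]/T = −k for any T, so the difference is 0.

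**Worked case, 14 against 17 hours.**
- Linear: 17/14 − 1 = 21.4%.
- k = 0.05: (1 − exp(−0.85))/(1 − exp(−0.70)) = 0.5726/0.5034 = 1.137, so +13.7%. Per hour: 1.137 × 14/17 = 0.937, so −6.3%.
- k = 0.15: (1 − exp(−2.55))/(1 − exp(−2.10)) = 0.9219/0.8775 = 1.051, so +5.1%. Per hour: 1.051 × 14/17 = 0.865, so −13.5%.

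| Waking hours | Linear, raw change | Exponential, raw change (k = 0.05 / 0.10 / 0.15) | Exponential, raw change per hour (same k) |
|---|---|---|---|
| 15 vs 16 | 6.7% | 4.4 / 2.7 / 1.6% | −2.2 / −3.7 / −4.7% |
| 14 vs 16 | 14.3% | 9.4 / 5.9 / 3.6% | −4.3 / −7.3 / −9.3% |
| 14 vs 17 | 21.4% | 13.7 / 8.5 / 5.1% | −6.3 / −10.7 / −13.5% |
| 13 vs 18 | 38.5% | 24.2 / 14.7 / 8.8% | −10.3 / −17.1 / −21.5% |

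Under linear decline the per-hour change removes the difference. Under exponential decline it does not: the dependence on waking span stays and changes sign, and at k = 0.15 it is larger than for the undivided change.

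**Share of variance.** Take raw change = b·T with b and T independent. The part of its variance that would vanish if everyone had the same span is 1 − CVb²/[(1 + CVb²)(1 + CVT²) − 1]. Assume a mean span of 16 hours.
- Span SD 1 hour (CVT = 0.0625), CVb = 0.5: 1 − 0.25/0.2549 = 1.9%.
- Span SD 2 hours (CVT = 0.125), CVb = 0.3: 1 − 0.09/0.1070 = 15.9%.

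So the range is about 2 to 16%.

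**The case against.** The strongest reply is that the words in parentheses are a gloss in a prose list, not a formula. The measure is called a slope, sample times are recorded, and the area under the curve, which also needs a time axis, is given no formula either. A per-hour rate may well have been intended. This stands in part: the text does not prove that the analyst will ignore time. But it does not say the opposite, and two analysts could produce two variables in different units under the same name. The allowance in Section 12.5 for transformations in the covariance models does not help, because transforming the finished difference does not bring time into it.

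The reply is also right that several stronger readings fail:
- A reader might infer that all the cortisol-anxiety correlations are affected. The mean levels and the awakening response do not use this definition, and nothing says that the area under the curve will ignore the recorded times.
- A reader might infer a very large distortion, such as 50% for a 12-hour against an 18-hour day (18/12 − 1). That needs an extreme pair and strictly linear decline. For the same pair, exponential decline at 0.05 to 0.15 per hour gives about 32% down to 12%.
- A reader might infer bias between arms. No section says that the device changes wake time or bedtime. Without such a shift, randomisation and baseline adjustment leave mainly noise, and sampling over three days dampens the day-to-day part.
- A reader might take division by hours as the obvious cure. The table shows that it is a full cure only if the decline is linear.

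**Conclusion.** As written, the diurnal slope mixes the length of the waking day into a measure named in Objective 1.5. The definition should be completed. The size rests wholly on assumed spans and decline shapes: for 14 against 17 waking hours, about 21% with linear decline and about 5 to 14% with exponential decline, and roughly 2 to 16% of the variance of the raw change under the linear model. For most participants the effect is probably modest.

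It reaches only the analyses that use the slope. It costs precision in the arm comparison and can confound the slope-anxiety correlations if anxiety goes with sleep timing. Dose selection and the decision on a phase III trial rest on anxiety and feasibility, and do not depend on it. This is a minor point, worth making because the correction is nearly free.

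**What to change.** In Section 12.5, define the diurnal slope as the slope of log cortisol on hours since awakening, from the diary-recorded sample times. Use the awakening and bedtime samples and leave the 30-minute sample to the awakening response. Either compute it per day and average over the three days of each visit, or fit it in a mixed model. Report the raw change per hour as a sensitivity measure: it is the span-free quantity if the decline is linear, where the log slope is not, so agreement between the two is informative. For clarity, state also that the area under the curve uses the recorded times.

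The cost is a sentence or two in the plan and a few lines of code, with no new data collection. The downsides are small. The measure is on a log scale, so a rule is needed for results below the assay sensitivity of 0.003 µg/dL given in Section 7.5.3. It also needs valid diary times, so the plan should say how a day with a missing or implausible time is handled.
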